## **Biostatistical Analysis**

### Study endpoints/variables

The primary endpoint of the study will be the change in PET uptake in the lesional and normal appearing white matter, cortical and subcortical grey matter, and peri-plaque area of chronic lesions in the brain at early and late time-points (5, 28, 90 and 273 days) as compared to baseline.

The secondary endpoints of the study will be the following:

- 1) Association of change in PET uptake in the lesional and normal appearing white matter, cortical and subcortical grey matter, and peri-plaque area of chronic lesions in the brain with changes in the peripheral CD19 counts, serum glial fibrillary acid protein (GFAP) and serum neurofilament light chain measurements at 5, 28, 90 and 273 days as compared to baseline.
- 2) Association of changes in PET uptake in the lesional and normal appearing white matter, cortical and subcortical grey matter, and peri-plaque area of chronic lesions in the brain with MRI and clinical changes at 5, 28, 90 and 273 days as compared to baseline.

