### Sample size and statistical considerations:

We will recruit 10 subjects, and each subject will undergo PET evaluations at day 0 (baseline), day 5, day 28, day 90 and day 273. The change with time in PET uptake in the lesional and normal appearing white matter, cortical and subcortical grey matter, and peri-plaque area of chronic lesions will be estimated using an analysis of response profiles model including a categorical effect of time and an unstructured covariance matrix for the residuals. This approach allows any change with time and places no structure on the covariance matrix. The primary analysis will be the global comparison across the five time points. If a significant difference among the five time points is observed, we will estimate the

change between day 0 and each of the other measurements, and we will correct for four multiple comparisons using a Bonferroni correction. Since the analysis of response profiles model estimates the parameters using maximum likelihood with the *mixed* command in Stata, this approach will handle missing data that is missing at random. Therefore, subjects who are missing one or more measurement will be included in our analysis. A p-value  $<0.05$  will be considered statistically significant.

In addition to the primary analysis of the change with time, we will also compare the change in PET uptake with the change in other measured variables (MRI, clinical, and immunologic measures). All of the remaining variables will be measured at the same time points as PET uptake (days 0, 5, 28, 90 and 273). First, we will calculate the change from day 0 to each of the other time points for each of the measures, and we will estimate the correlation between the changes using Pearson's correlation coefficient. This analysis will fit several models, but the interpretation of these correlations will be easy to interpret. Second, we will fit a linear mixed model with PET uptake as the outcome and two predictors for each of the other measured variables. In particular, we will include (1) the day 0 measure and (2) the change from day 0 so that we can estimate both the cross-sectional and longitudinal association between the other measured variables and PET. Our focus will be the longitudinal association estimated using the second term. If a subject receives corticosteroids during the study period, we'll account for that in a multivariate analysis by adding it as a covariate.

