Paired t-test and repeated measures ANOVA analyses will be performed to assess differences in PET measures over time. Correlation analyses will be performed between PET and MRI measures and clinical variables. We will also look for correlations between changes in PET uptake and peripheral CD19 counts at various time points of the study.

Statistical analyses will be performed using Stata version 16 (StataCorp, College Station, Texas, USA).

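### The primary mixed-model test has no small-sample method for 10 subjects, so its nominal 5% error rate is about 16-33% under the usual large-sample tests; the added t-tests and ANOVA also need a stated role

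*Combined protocol and SAP*

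**What the plan says.** All references are to the Combined protocol and SAP, Biostatistical Analysis.

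- **Model.** Under Sample size and statistical considerations, PET uptake is analysed with a response-profiles model "including a categorical effect of time and an unstructured covariance matrix for the residuals". The model "estimates the parameters using maximum likelihood" in Stata, so that subjects with missing visits stay in.
- **Order of testing.** "The primary analysis will be the global comparison across the five time points". Only if that test is significant are the four changes from day 0 estimated, and then "we will correct for four multiple comparisons using a Bonferroni correction". That gives 0.05/4 = 0.0125 each.
- **Threshold.** A p-value below 0.05 "will be considered statistically significant". The plan does not name the global test statistic (Wald chi-square, likelihood ratio or F) or any small-sample adjustment.
- **Added tests.** The closing paragraph of the same subsection says: "Paired t-test and repeated measures ANOVA analyses will be performed to assess differences in PET measures over time". It gives no role, visit pairs, dependence on the global test or correction.
- **Endpoint.** Study endpoints/variables defines the primary endpoint as change in PET uptake "at early and late time-points (5, 28, 90 and 273 days) as compared to baseline".

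**The concern.** **Main point.** An unstructured covariance over five visits has 5 x 6 / 2 = 15 variance and covariance parameters, estimated here from 10 subjects. Maximum likelihood understates the variances (divisor 10 instead of 9). The chi-square and normal reference distributions also treat the estimated covariance as known. Both errors make p-values too small. The global test is the primary analysis and also decides whether the day-0 contrasts are examined, so an inflated global test weakens the whole scheme. The study is open-label with a single group, so these within-subject tests carry the inference.

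**Minor point.** The t-tests and ANOVA address the same question outside the stated order. The general 0.05 threshold is the only one available to them. A t-test could therefore be reported as significant when the planned global test is not.

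**Working it through.** **Inputs.** n = 10, five visits, threshold 0.05, four day-0 contrasts at 0.0125 (Sample size and statistical considerations); effect size 1.1 (Sample size calculation). Assumptions not in the documents: two-sided tests, normal data, complete data, one region at a time.

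**1. The plan's own figures.** The standard error is 1/sqrt(10) = 0.316, which matches the stated 0.32. Power of a two-sided paired t-test at effect size 1.1 (noncentral t, 9 df) is 87.1% at 0.05, close to the stated 85%. A signed-rank version with efficiency 0.955 gives 85.1%. The plan does not name the test behind its figure. At 0.0125 the paired t-test has 64.6% power.

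**2. True size of the global test.** With complete data, every version is a function of Hotelling's T2 for the four changes from day 0. Under the null, T2 x (10 - 4)/(4 x 9) = T2/6 follows F(4, 6) exactly, whatever the covariance. The 5% chi-square point on 4 df is 9.488.

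| Global test | Rejects when | T2 above | T2/6 above | True size |
|---|---|---|---|---|
| ML Wald chi-square | T2 x 10/9 > 9.488 | 8.539 | 1.423 | 33.2% |
| ML likelihood ratio | 10 ln(1 + T2/9) > 9.488 | 14.243 | 2.374 | 16.5% |
| REML Wald chi-square | T2 > 9.488 | 9.488 | 1.581 | 29.3% |
| REML Wald F, unscaled, on 4 and 9 df | T2/4 > 3.633 | 14.532 | 2.422 | 16.0% |
| Hotelling T2 (scaled F on 4 and 6 df) | T2/6 > 4.534 | 27.202 | 4.534 | 5.0% |

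**3. The day-0 contrasts.** A normal-based contrast at 0.0125 rejects when |z| > 2.498. With the ML variance, z = t x sqrt(10/9), so this is |t| > 2.498 x sqrt(0.9) = 2.370. On 9 df the two-sided probability is 4.2%, not 1.25%.

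**4. The whole rule (global test, then 0.0125).** This depends on the correlation between visits, so it was simulated: 200,000 null trials for each of five assumed patterns (compound symmetry 0.5 and 0.8; AR(1) 0.7; exponential decay with a 90-day scale, with and without 20% scan noise). The chance of at least one false day-0 contrast is:
- 11.0-13.5% with the Wald test and z contrasts;
- 7.0-8.7% with the likelihood-ratio test and z contrasts;
- 1.6-1.9% with the exact test and t contrasts.

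**5. The added tests, same simulations.**
- Any of four day-0 paired t-tests below 0.05: 16.1%, 16.2%, 14.3%, 17.3%, 17.0% across the five patterns. At 0.0125: 4.1-4.7%.
- Any such t-test below 0.05 while the global test is not significant: 1.9-2.1% (Wald), 6.6-7.8% (likelihood ratio), 11.6-14.0% (exact).
- Repeated measures ANOVA: 5.0-8.4% without a sphericity correction, 2.9-4.1% with Greenhouse-Geisser.

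**The case against.** **The global statistic is not named, so 33% is not a fact about the plan.** This stands in part. The true figure depends on the statistic used. But both usual tests from a maximum-likelihood fit are well above 5%, and the small-sample remedy below is built on REML, which the plan does not specify. It cannot be assumed.

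**This is a 10-subject study meant to inform later designs.** That is a fair reason not to demand confirmatory rigour. Still, the plan chose a primary test, a 0.05 threshold and a Bonferroni correction, and the estimation method undoes them.

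**The t-test and ANOVA sentence may only be a summary.** This largely stands. The neighbouring sentences on correlations with MRI, clinical variables and CD19 largely repeat what the mixed-model text already plans. With complete data, a day-0 contrast in an unstructured model has the same estimate as the paired mean difference. The sentence does not refer back, however. The methods also differ when visits are missing: paired t-tests drop a subject who lacks either visit, and the mixed model does not.

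**Stronger readings that the documents do not support.** A reader might infer that the added tests are a second confirmatory route that inflates the primary error rate. The plan names one primary analysis, and extra tests do not change that test's error rate. A reader might also quote 64% for four tests in each of five regions (1 - 0.95^20). That assumes independence, but regions and visits are correlated. Nor is the 12-14% discordance the harm in the plan as written, because it arises only against an exact global test. Under the large-sample tests it is about 2-8%.

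**Conclusion.** The main point holds: as written, the primary analysis does not deliver its stated 5% level. Per region, the global test rejects a true null in about 33% of trials (Wald) or 16-17% (likelihood ratio). The full rule gives a false day-0 contrast in about 11-14% or 7-9%. The global figures need normality and complete data but no assumption about correlation. The figures for the full rule rest on the five assumed patterns. Missing visits would change the exact values.

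The unstated role of the t-tests and ANOVA is a minor clarification. If four day-0 t-tests were judged at 0.05, the chance of a false positive would be 14-17% per region under those patterns, against 4-5% at 0.0125. The text shows an ambiguity, not a decision to test that way.

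**What to change.** **Primary analysis.** Keep the model and the data. Fit by REML, use the Kenward-Roger scaled F for the global test and t-based day-0 contrasts at 0.0125, and name the global test statistic. With complete data, Hotelling's T2 is an exact alternative (size 5%). REML alone still rejects a true null in 29% of trials. Changing only the denominator degrees of freedom, without rescaling the statistic, still rejects in 16%. The text must therefore specify the scaled F, not just a degrees-of-freedom method.

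**Added tests.** Add one sentence: the paired t-tests and repeated measures ANOVA are supportive, and claims of significance rest on the mixed model with its global test first and the 0.0125 level. A Greenhouse-Geisser correction for the ANOVA is optional.

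**Cost.** The changes are to the estimation and testing method and a few lines of wording; no new data are needed. P-values become less favourable. With an effect of 1.1 at all four visits or only at day 273, power of the global test is 57-88% (exact), against 85-99% (likelihood ratio) and 96-99.9% (Wald) under the assumed patterns. Part of that large-sample advantage is the inflated error rate.

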#### Sample size calculation:

No prior data regarding effect of Ofatumumab on microglial changes is available at this time. The sample size of 10 is based on the typical number of patients in published PET-MRI studies with the same tracer. With a sample size of 10 subjects, we will be able to estimate the mean change between any pair of time points with a standard error of 0.32 times the standard deviation of the change. Assuming a PET effect size of 1.1 noticeable in intracortical and leukocortical lesions, identified on combination of PET and 3T MRI, a sample size of 10 provides 85% power and alpha-error of less than 5% to detect a treatment response. This means that we will have a reasonable precision for the design of future studies.

